7.5.3 Objective Response Rate

7.5.3.1 Primary Analysis of ORR

BOR will be summarized by response category for each treatment group. ORR will be computed in each treatment group along with the exact 95% CI using Clopper-Pearson method¹⁷.

An estimate of the difference in ORRs and corresponding 95% CI will be calculated using CMH methodology and adjusted by the same stratification factors as for primary analysis of OS.

In addition, the stratified (source: IVRS) odds ratios (Mantel-Haenszel estimator) between the treatments will be provided along with the 95% CI. The difference will be tested via the Cochran Mantel-Haenszel (CMH) test using a two-sided, 5% α level.

To assess consistency of treatment effect on ORR in different subsets, ORR will be computed across the same subsets as defined in the OS analysis (see [Section 7.5.1.3](#)).

7.5.3.2 Sensitivity Analyses of ORR

If one stratification variable at IVRS and at baseline (CRF) disagrees for at least 10% of the randomized subjects, similar analysis of ORR as primary analysis will be performed using the strata as determined at baseline.

7.5.4 Duration of Objective Response

Duration of response in each treatment group will be estimated using KM product-limit method for subjects who achieve PR or CR. Duration of stable disease will also be estimated in each treatment groups using KM product-limit method for subjects with SD as best response. Median values along with two-sided 95% CI will be calculated. Summary statistics will be computed constructed based on a log-log transformed CI for the survivor function S(t).

7.5.5 Time to Objective Response

Summary statistics of time to objective response will be provided for each treatment group for subjects who achieve PR or CR.

To assess further tumor response kinetics, time to response will be analyzed using the KM methodology, for all randomized subjects. Kaplan-Meier curve will represent the cumulative rate of response over time. For the non-responders, time to response will be censored at the maximum time of response + 1 day of all subjects in their respective treatment group. Cumulative Response Rates will be tabulated for Week 6, Month 4, 6, 8, and 12, and overall Response Rate will be provided for each treatment group.

7.5.6 Hierarchy for Key Secondary Efficacy Endpoints

In order to preserve an experimental-wise type I error rate at 5%, a pre-planned hierarchy for key secondary endpoints will be applied when interpreting the statistical significance of treatment comparisons. The hierarchical ordering of the key secondary endpoints is as follows:

- 1) Progression-Free Survival
- 2) Objective Response Rate

The statistical testing will be carried out using the following sequential procedure:

- 1) The primary endpoint of OS will be tested first.
- 2) If the p-value of OS is not statistically significant against nominal significance level either at interim or final analysis, then no further statistical testing regarding the secondary endpoints will be conducted. However estimates along with their 95% CI will be provided for those (i.e. medians and HR, rates and odds ratio)
- 3) If the p-value of OS is statistically significant against nominal significance level either at interim or final analysis, the secondary endpoint with the highest ranking in the hierarchy will be tested (PFS in this case). If the p-value of PFS is statistically significant at 5% level, the second highest ranking endpoint in the hierarchy will be tested (ORR in this case) and the p-value of ORR will be provided. If the p-value of PFS is not statistically significant at 5% level, then no further statistical testing regarding the other secondary endpoint (i.e., ORR) will be conducted. Estimates (medians and HR) and their 95% CI will be provided for ORR regardless of the outcome of PFS testing.

7.5.7 Follow-up Therapy

Number and percentage of subjects receiving subsequent therapies including radiotherapies, surgeries and systemic therapies will be reported.

Subsequent therapies will be summarized and listed.

- Subsequent Therapy
 - Chemotherapy by drug name
 - Hormonal or biologic therapy by drug name
 - Immunotherapy (anti-PD1 agents, anti-CTLA4 agents and others, by drug name)

- Tyrosine kinase inhibitor by drug name
- Other investigational agent by drug name
- Surgery
- Radiotherapy
- Any combination of the above
- By Subject Listing of Subsequent Therapy

7.5.8 Other Efficacy Analyses

The following subject-level graphics will also be provided by treatment group as randomized:

- For the responders only, time courses of the following events of interest will be graphically displayed: tumor response, tumor progression, last dose received, and death.
- For response evaluable subjects, a waterfall plot showing the best reduction in target lesion will be produced.

7.5.9 Interim Analysis

No formal Analysis will be run

7.6 Safety

7.6.1 Deaths

See Core Safety SAP

7.6.2 Serious Adverse Events

See Core Safety SAP

7.6.3 Adverse Events Leading to Discontinuation of Study Therapy

See Core Safety SAP

7.6.4 Adverse Events Leading to Dose Delay of Study Therapy

See Core Safety SAP

7.6.5 Adverse Events

See Core Safety SAP

7.6.6 Adverse Events by Subgroups

See Core Safety SAP

7.6.7 Multiple Events

See Core Safety SAP

7.6.8 Adverse Events of Special Interest

See Core Safety SAP

7.6.9 Clinical Laboratory Evaluations

The analysis population for each laboratory test is restricted to treated subjects who underwent that laboratory test.

7.6.9.1 Hematology

See Core Safety SAP

7.6.9.2 Serum Chemistry

See Core Safety SAP

7.6.10 Vital Signs and Pulse Oximetry

See Core Safety SAP

7.6.11 Immunogenicity Analysis

Nivolumab arm only. See Core Safety SAP

7.6.12 Pregnancy

By-subject listing of pregnancy tests results will be provided

7.6.13 Clinical Safety Program (CSP)

See Core Safety SAP

7.7 Pharmacokinetics

Pharmacokinetics analyses will be performed on nivolumab arm only.

The concentration vs. time data obtained in this study will be combined with data from other studies in the clinical development program to develop a population PK model. This model will be used to evaluate the effects of intrinsic and extrinsic covariates on the PK of nivolumab and to determine measures of individual exposure (such as steady-state peak, trough, and time-averaged concentration). Model determined exposures will be used for exposure-response analyses of selected efficacy and safety end points. Results of population PK and exposure-response analyses will be reported separately.

[Redacted text block]

7.8.1.3 Association between TMB and Efficacy

[Redacted text block]

7.9 Outcomes Research Analyses

The outcome research analyses will be performed using all randomized subjects.

7.9.1 LCSS questionnaire

LCSS questionnaire completion rate, defined as the proportion of questionnaires actually received out of the expected number (i.e., the number of subjects still on treatment or in follow-up), will be calculated and summarized at each assessment point.

Baseline and change from baseline of the average symptom burden index score at each assessment point will be summarized using descriptive statistics (N, mean, median, SD, 25th and 75th percentiles) by treatment group, as randomized.

Kaplan-Meier plots for TTD in symptoms as measured by LCSS ASBI would be presented along with median TTD and corresponding 95% CI.

TTD rates at fixed timepoints Week 6, 12 and 24 will be derived from the Kaplan Meier estimate and corresponding confidence interval will be derived based on Greenwood formula¹⁸ for variance derivation and on log-log transformation applied on the survivor function $S(t)$ ¹⁹.

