3.1.1.3 Follow up

- Begins when the decision to discontinue a subject from study drug is made (no further treatment with study drug).
- Follow-up consists of 2 follow-up visits within approximately 100 days of the last dose of study drug followed by survival visits that will continue every 3 months after Follow-up Visit 2 until death, lost to follow-up, or withdrawal of study consent.
- Subjects who discontinue study drug for reasons other than disease progression will continue to have radiographic assessments every 6 weeks (± 5 days) for the first 30 weeks, and subsequently every 12 weeks (± 5 days), until disease progression (or until discontinuation of study drug in subjects receiving nivolumab beyond progression), lost to follow-up, withdrawal of study consent, or the study ends.

Study assessments are to be collected as outlined in [Table 5.1-4](#).

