| blood, tumor biopsy) | | | progression is optional. See Table 5.6-1 or Table 5.6-2 of Biomarker Sampling Schedule. |
| Outcomes Research Assessments | | | |
| Patient Reported Outcomes (PRO) | X | EQ-5D only | Both the Lung Cancer Symptom Scale and EQ-5D will be given in Follow-up Visits 1 & 2. In Survival Visits, EQ-5D is collected every 3 months for the first year of the Follow-up Phase, then every 6 months thereafter. |
| Subject Status | | | |
| Survival Status | X | X | Every 3 months after X02; may be accomplished by visit or phone contact, to update survival information and assess subsequent anti-cancer therapy. |

ALP = alkaline phosphatase, ALT = alanine aminotransferase, AST = aspartate aminotransferase, BP = blood pressure, BUN = blood urea nitrogen, Ca = calcium, Cl = chloride, CT = computed tomography, ECG = electrocardiogram, IVRS = interactive voice response system, K = potassium, LDH = lactate dehydrogenase, Mg = magnesium, MRI = magnetic resonance imaging, Na = sodium, NCI CTCAE = National Cancer Institute Common Toxicity Criteria for Adverse Events, O2 = oxygen, P = phosphorus, SAE = serious adverse event, T.Bili = total bilirubin, TSH = thyroid stimulating hormone, T3 = triiodothyronine, T4 = thyroxine, WOCBP = women of childbearing potential

^a Follow-up visits occur as follows: X01 = 35 days (\pm 7 days) from last dose, X02 = 80 days (\pm 7 days) from X01

^b S, Survival visits continue every 3 months (\pm 7 days) after Follow-up Visit 2 until death, lost to follow-up, or withdrawal of study consent

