8.4.6 Outcomes Research Analyses

LCSS questionnaire complete rate, defined as the proportion of questionnaires actually received out of the expected number (ie, the number of subjects still on treatment or in follow-up), will be calculated and summarized at each assessment point.

Baseline and change from baseline of the average symptom burden index score at each assessment point will be summarized using descriptive statistics.

Subject's overall health state on a visual analog scale (EQ-VAS) at each assessment time point will be summarized using descriptive statistics. Proportion of subjects reporting problems for the 5 EQ-5D dimensions at each assessment time point will be summarized by level of problem.

Summary statistics will be calculated for the population preference-based health state utility score (EQ-5D Index).

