7.9.2 EQ-5D questionnaire

AS done for LCSS, EQ-5D questionnaire completion rate, defined as the proportion of questionnaires actually received out of the expected number (i.e., the number of subjects still on treatment or in follow-up), will be calculated and summarized at each assessment point.

Subject's overall health state on a visual analog scale (EQ-VAS) at each assessment time point will be summarized along with change from baseline using descriptive statistics (N, mean, SD, median, 25th and 75th percentiles) by treatment group, as randomized.

Subject's overall health state on EQ-5D index using UK weighting algorithm at each assessment time point will be summarized along with change from baseline using descriptive statistics (N, mean, SD, median, 25th and 75th percentiles) by treatment group, as randomized.

Proportion of subjects reporting problems for the 5 EQ-5D dimensions at each assessment time point will be summarized by level of problem and by treatment group, as randomized. Percentages will be based on number subjects assessed at assessment time point.

A by-subject listing of EQ-5D with the problem levels for each of the 5 dimensions (mobility, self-care, usual activities, pain/discomfort and anxiety/depression), health state (5 dimensions digits combined in a 5-digit number) and EQ-VAS will be provided.

Results of EQ5D-Index will be presented separately and will be described in the GHEOR SAP.

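### The LCSS completion rate counts as expected all subjects on treatment or in follow-up, although no LCSS is scheduled at survival visits, so scheduled non-collection reads as non-completion

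*SAP*

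**What the plan says.** SAP 7.9.1 defines the LCSS completion rate as questionnaires received "out of the expected number (i.e., the number of subjects still on treatment or in follow-up". The rate "will be calculated and summarized at each assessment point". Protocol 8.4.6 gives the same denominator: "out of the expected number (ie, the number of subjects still on treatment or in follow-up". SAP 7.9.2 carries it over to the other instrument: "AS done for LCSS, EQ-5D questionnaire completion rate".

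The collection schedule is in the protocol:

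- **On treatment** (Tables 5.1-2 and 5.1-3): LCSS and EQ-5D on Day 1 of each cycle for the first 6 months, then every 6 weeks while treatment lasts.
- **Follow-up Visits 1 and 2** (Table 5.1-4): "Both the Lung Cancer Symptom Scale and EQ-5D will be given in Follow-up Visits 1 & 2".
- **Survival visits** (Table 5.1-4): EQ-5D only. "In Survival Visits, EQ-5D is collected every 3 months for the first year of the Follow-up Phase", and every 6 months after that.

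Protocol 3.1.1.3 sets the extent of the follow-up phase: "Follow-up consists of 2 follow-up visits within approximately 100 days of the last dose of study drug followed by survival visits". The survival visits continue every 3 months until death, loss to follow-up or withdrawal of consent.

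**The concern.** A completion rate should show how many of the questionnaires that were due came back. Here the parenthesis equates the expected number with everyone on treatment or in follow-up. That group includes subjects from whom the schedule no longer asks for an LCSS. They add to the denominator and cannot add to the numerator.

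Readers use the completion rate to judge how far missing data may affect the LCSS results, and in an open-label trial they will compare it between arms. As defined, it mixes non-response with planned non-collection. Low completion could then be reported where compliance was good. An apparent difference between arms could likewise reflect only different times on treatment.

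**Working it through.** The documents state no completion rate, expected count or time on treatment, so there is no plan figure to reproduce. The check compares the denominator with the schedule and then illustrates the size.

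**1. When LCSS collection ends.** Table 5.1-4 puts Follow-up Visit 1 at 35 days after last dose and Visit 2 at 80 days after Visit 1, each ± 7 days.

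- Nominal: 35 + 80 = 115 days after last dose, and 115 / 7 = 16.4 weeks.
- With windows: 28 + 73 = 101 days to 42 + 87 = 129 days.

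A subject who stops after one dose therefore passes Visit 2 at about Week 16. Protocol 3.1.1.3 places both visits within approximately 100 days of last dose, which would be about Week 14 (100 / 7 = 14.3). Before then no subject can be in survival follow-up.

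**2. Who is counted but not due.**

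- *Past Visit 2:* in the follow-up phase by protocol 3.1.1.3, with no LCSS scheduled. This applies from about Week 16.
- *Off treatment, not yet past Visit 2:* due at two visits only. If they are also counted at on-treatment cycle visits, they are not due there. This can apply from the first weeks.

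**3. Effect on the rate.** Let c be the completion among those due and s the share of the denominator not due. Then reported rate = c × (1 − s). Assume c = 0.90, and s = 0.20 to 0.50 in survival follow-up at a point from about Week 16 on:

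- 0.90 × (1 − 0.20) = 0.72
- 0.90 × (1 − 0.50) = 0.45

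**4. Illustration by time on treatment.** From the documents: 50% OS at 8 months in both arms with HR = 1 to Month 8 (protocol Table 8.1-1), taken here as exponential survival. Assumed: c = 0.90, exponential time on treatment with median m months, and the same death hazard on and off treatment. With h = ln2/m − ln2/8 and t in months, among subjects alive at t:

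- share on treatment = exp(−h·t)
- share in survival follow-up = 1 − exp(−h·(t − 115 days))

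At Week 24, t = 168 / 30.4375 = 5.52 months and 115 days = 3.78 months, a difference of 1.74 months.

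| | m = 2 | m = 4 |
|---|---|---|
| h per month | 0.260 | 0.087 |
| Week 24: in survival follow-up | 36% | 14% |
| Week 24: reported rate, Visit 1–2 subjects treated as due | 57% | 77% |
| Week 24: reported rate, only on-treatment subjects due | 21% | 56% |
| Week 12: in survival follow-up | 0% | 0% |
| Week 12: reported rate, only on-treatment subjects due | 44% | 71% |

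True completion is 90% in every cell. If two arms had medians of 2 and 4 months, survival follow-up alone would produce a 20-point gap at Week 24 (77% − 57%). Over medians of 1.5 to 5 months, the Week 24 rate on the same basis runs from 47% to 82%.

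**5. After the change.** With the denominator limited to subjects due an LCSS, s = 0 and the rate returns to 90% whatever the time on treatment.

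**The case against.** The main defence is a distributive reading. The rate is computed at assessment points, and a survival visit is not an LCSS assessment point. On this reading the definition means on-treatment subjects at cycle visits and follow-up subjects at Visits 1 and 2. Table 5.1-4 does give these two visits and the survival visits separate columns. The programming may also follow this reading, since the table mock-ups sit in a Data Presentation Plan outside these documents. The reading is possible, but the text does not state it. The parenthesis defines the expected number without reference to who is due, and protocol 3.1.1.3 includes survival visits in follow-up. Taken literally, one denominator also cannot fit both LCSS and EQ-5D, whose schedules differ after Visit 2.

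Three further points carry weight:

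- SAP 7.9.1 reports N at each assessment point by arm, and SAP 7.4.1 gives Kaplan-Meier duration of treatment. These help a reader see attrition, although neither gives the number due.
- A rate among those due can look high while most living subjects contribute no LCSS. SAP 7.9 analyses all randomized subjects, so that share is informative too and should not disappear.
- The survival follow-up effect is absent at Weeks 6 and 12. Of the three fixed LCSS time points in SAP 7.9.1, it can reach only Week 24.

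A reader might infer that completion will be lower in the chemotherapy arm. The documents do not support that. Protocol 1.1.5 mentions different durations of therapy, and protocol 4.5.4 lets only Arm A continue past progression, under conditions. Neither states which arm stops earlier, and no expected time on treatment is given.

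**Conclusion.** The point holds as a mismatch between the stated denominator and the collection schedule. Applied literally, the rule understates LCSS completion. It does so from about 16 weeks after first dose for subjects past Follow-up Visit 2, and earlier if off-treatment subjects are counted at cycle visits.

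The direction follows from the documents; the size does not. The 72% to 45% range rests on an assumed 90% completion among those due and on 20% to 50% of living subjects being in survival follow-up. It should not be read as applying before about Week 16. A difference between arms with identical compliance is possible if time on treatment differs, but it is conditional on that.

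A reader might also infer that the LCSS results themselves are distorted. They are not: change from baseline and time to deterioration do not use this denominator, and no test, imputation or decision rule depends on it. OS, alpha and power are unaffected. This is a minor point about a descriptive measure for an exploratory endpoint.

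**What to change.** - **SAP 7.9.1 and protocol 8.4.6:** define expected as subjects who are alive, in study and scheduled for an LCSS at that assessment point under protocol Tables 5.1-2 to 5.1-4, with Follow-up Visits 1 and 2 as their own points. Changing the SAP alone would leave the two documents in disagreement.
- **SAP 7.9.2:** give EQ-5D its own schedule-based denominator, including survival visits where EQ-5D is scheduled.
- **Both instruments:** also report the proportion of all living randomized subjects with a questionnaire at each point, so that loss of data after treatment stops stays visible.

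The cost is small: a sentence in each section, a denominator flag, one extra table row and the matching protocol edit. The dosing, visit and survival dates needed are already collected.

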7.9.2 EQ-5D questionnaire

AS done for LCSS, EQ-5D questionnaire completion rate, defined as the proportion of questionnaires actually received out of the expected number (i.e., the number of subjects still on treatment or in follow-up), will be calculated and summarized at each assessment point.

Subject's overall health state on a visual analog scale (EQ-VAS) at each assessment time point will be summarized along with change from baseline using descriptive statistics (N, mean, SD, median, 25th and 75th percentiles) by treatment group, as randomized.

Subject's overall health state on EQ-5D index using UK weighting algorithm at each assessment time point will be summarized along with change from baseline using descriptive statistics (N, mean, SD, median, 25th and 75th percentiles) by treatment group, as randomized.

Proportion of subjects reporting problems for the 5 EQ-5D dimensions at each assessment time point will be summarized by level of problem and by treatment group, as randomized. Percentages will be based on number subjects assessed at assessment time point.

A by-subject listing of EQ-5D with the problem levels for each of the 5 dimensions (mobility, self-care, usual activities, pain/discomfort and anxiety/depression), health state (5 dimensions digits combined in a 5-digit number) and EQ-VAS will be provided.

Results of EQ5D-Index will be presented separately and will be described in the GHEOR SAP.

8 CONVENTIONS

The following conventions may be used for imputing partial dates for analyses requiring dates:

- For missing and partial adverse event onset dates, imputation will be performed using the Adverse Event Domain Requirements Specification²⁰.
- Missing and partial Non-Study Medication Domain dates will be imputed using the derivation algorithm described in Section 4.3.3 of BMS Non-Study Medication Domain Requirements Specification²¹.

For death dates, the following conventions will be used for imputing partial dates:

- If only the day of the month is missing, the 1st of the month will be used to replace the missing day. The imputed date will be compared to the last known date alive and the maximum will be considered as the death date.
- If the month or the year is missing, the death date will be imputed as the last known date alive. If the date is completely missing but the reason for death is present the death date will be imputed as the last known date alive

For date of progression, the following conventions will be used for imputing partial dates:

- If only the day of the month is missing, the 1st of the month will be used to replace the missing day*.
- If the day and month are missing or a date is completely missing, it will be considered as missing.
- In case of the date of death is present and complete, the imputed progression date will be compared to the date of death. The minimum of the imputed progression date and date of death will be considered as the date of progression.
- For other partial/missing dates, the following conventions may be used:
- If only the day of the month is missing, the 15th of the month will be used to replace the missing day.
- If both the day and the month are missing, “July 1” will be used to replace the missing information.
- If a date is completely missing, it will be considered as missing.

The following conversion factors will be used to convert days to months or years:
1 month = 30.4375 days and 1 year = 365.25 days.

Duration (e.g. time from first diagnosis of SCLC to first dosing date, duration response, and time to response) will be calculated as follows:

$$\text{Duration} = (\text{Last date} - \text{first date} + 1)$$

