3.6.2 Lost to Follow-Up

All reasonable efforts must be made to locate subjects to determine and report their ongoing status. This includes follow-up with persons authorized by the subject as noted above. Lost to follow-up is defined by the inability to reach the subject after a minimum of three documented phone calls, faxes, or emails as well as lack of response by subject to one registered mail letter. All attempts should be documented in the subject's medical records. If it is determined that the subject has died, the site will use permissible local methods to obtain the date and cause of death.

If investigator's use of third-party representative to assist in the follow-up portion of the study has been included in the subject's informed consent, then the investigator may use a Sponsor-retained third-party representative to assist site staff with obtaining subject's contact information or other public vital status data necessary to complete the follow-up portion of the study. The site staff and representative will consult publicly available sources, such as public health registries and databases, in order to obtain updated contact information. If after all attempts, the subject remains lost to follow-up, then the last known alive date as determined by the investigator should be reported and documented in the subject's medical records.

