5.4.1 Primary Efficacy Assessment

The primary endpoint is OS in all randomized subjects. See [Section 8.3.1](#) for the definition of OS. Every effort will be made to collect survival data on all subjects including subjects

withdrawn from treatment for any reason, who are eligible to participate in the study and who have not withdrawn consent for survival data collection. If the death of a subject is not reported, all dates in this study representing a date of subject contact will be used in determination of the subject's last known date alive.

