8.3 Endpoints

8.3.1 Primary Endpoint(s)

The primary endpoint for the study is OS. It is defined as the time from randomization to the date of death. A subject who has not died will be censored at last known date alive. OS will be followed continuously while subjects are on the study drug and every 3 months via in-person or phone contact after subjects discontinue the study drug.

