4 ENDPOINTS

4.1 Primary Endpoints

[figure not shown]
OS is defined as the time from randomization to the date of death. A subject who has not died will be censored at last known date alive.

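### A death recorded with a year but no month can be dated before that year, because the SAP falls back on the last known date alive

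*SAP*

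**What the plan says.** SAP section 8 (Conventions) makes its death-date rules binding: "For death dates, the following conventions will be used for imputing partial dates". There are three cases.

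- **Only the day missing.** The first of the recorded month is used, and then: "The imputed date will be compared to the last known date alive and the maximum will be considered as the death date".
- **Month or year missing.** "If the month or the year is missing, the death date will be imputed as the last known date alive".
- **Whole date missing, reason for death present.** The last known date alive is used.

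For dates other than death and progression, the same section has an optional convention. It begins "If both the day and the month are missing" and puts the date at 1 July, so a recorded year is kept. Progression dates without a day and month are treated as missing.

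The death date drives the primary endpoint: "OS is defined as the time from randomization to the date of death" (SAP 4.1). Off treatment, survival status is collected "every 3 months via in-person or phone contact after subjects discontinue the study drug" (Protocol 8.3.1), with a window of 7 days either side (Protocol Table 5.1-4, footnote b). For the last known date alive, Protocol 5.4.1 says "all dates in this study representing a date of subject contact will be used in determination of" it. That sentence is written for subjects with no reported death; I take the same definition to apply here. The Protocol contains no death-date imputation rule that overrides the SAP.

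**The concern.** When the day is missing, the SAP keeps what was recorded (month and year) and uses the last known date alive only as a lower limit. When the month is missing, it drops the recorded year and makes no check against it. An OS event can then carry a date that the source record rules out.

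The same date enters PFS for subjects who die without progression (SAP 4.2.1), the OS rates at fixed months (SAP 7.5.1.1), and the piecewise hazard ratios, for which the SAP's example splits at 8 months (SAP 7.5.1.2). A death moved earlier could cross one of those time points. The questions are which deaths are misdated in this sense, how many there might be, and whether the primary result could move.

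**Working it through.** **1. The plan's own figures.** The imputation rule has no stated figure, so I first checked the design model used below.

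- Power with 482 events and average HR 0.745: √482 / 2 × |ln 0.745| − 1.960 = 10.977 × 0.2944 − 1.960 = 1.271, and Φ(1.271) = 89.8%. The plan states 90%.
- Control hazards: ln 2 / 8 = 0.0866 per month up to month 8, then ln(0.50/0.05) / 16 = 0.1439. Nivolumab survival at 24 months: 0.5 × exp(−0.5 × 0.1439 × 16) = 15.8%. The plan states 16%.
- With uniform accrual and no dropout, the model gives about 500 deaths at 34 months against the stated 482. An accrual ramp or censoring that the plan does not state could explain this. It does not affect the point here.

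**2. When the recorded year is contradicted.** Let L be the last known date alive and Y the recorded year of death. The earliest date compatible with the record is max(1 January Y, L). The SAP returns L.

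- L within Y: max(1 January Y, L) = L. The SAP already gives the earliest compatible date.
- L before Y: max(1 January Y, L) = 1 January Y. The SAP gives a date in the wrong year.

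Example: L = 20 November 2017, Y = 2018. There are 11 days to 1 December and 31 more to 1 January, so the SAP date is 42 days before the earliest possible one.

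**3. How many deaths.** Two inputs are assumptions, because the documents give neither.

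- Share of deaths with the month missing but the year known: 0.5% to 2%. That is 0.005 × 482 = 2.4 to 0.02 × 482 = 9.6 deaths.
- Gap from last contact to death: uniform on 0-3, 0-6 or 0-12 months, cut off at randomization. The scheduled interval is about 3 × 30.4375 + 7 = 98 days.

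The design model was simulated (6,000 runs per gap, random calendar start, month-missing deaths drawn at random with the same probability in both arms). As a hand check, if deaths fall evenly over the year, the chance that 1 January lies between last contact and death is the mean gap divided by 12: 1.36/12 = 11%, 2.49/12 = 21%, 4.16/12 = 35%. The simulation agrees.

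| Assumed gap | Mean gap per affected death | Share with last contact before the recorded year | Deaths redated (0.5% to 2%) | Mean move later in those deaths |
|---|---|---|---|---|
| 0-3 months | 1.36 months | 11.4% | 0.3 to 1.1 | 0.95 months |
| 0-6 months | 2.49 months | 20.7% | 0.5 to 2.0 | 1.81 months |
| 0-12 months | 4.16 months | 34.6% | 0.8 to 3.3 | 3.25 months |

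**4. Effect on the trial.** These are the simulated differences between the SAP rule and max(1 January Y, L).

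- At 2% month-missing and gaps of 0-12 months: medians 7.821 vs 7.844 (control) and 8.058 vs 8.080 (nivolumab), a change of about 0.02 months.
- At 5% and 0-12 months: at most 0.07 months.
- At 10% and 0-12 months, well outside the assumed range: 0.13 to 0.14 months.
- Power differs by no more than 0.14 percentage points in any scenario run.

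**The case against.** The strongest reply is that early dating is the SAP's consistent convention for deaths, and that the remedy shares it. The first of the month is the earliest date in a known month, and 1 January is the earliest date in a known year. Where last contact fell in the year of death, the remedy also leaves the death on a day of documented contact. This stands. Early dating as such is not the defect; only the contradiction with a recorded year is.

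The Protocol also limits exposure to the rule. The sponsor may request survival data outside the visit window (3.6). For subjects lost to follow-up, "If it is determined that the subject has died, the site will use permissible local methods to obtain the date and cause of death" (3.6.2). Deaths on treatment are collected as serious adverse events and reported within 24 hours of awareness (6.1, 6.1.1). These steps make a missing month less likely, but they do not correct the rule when it applies.

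A reader might infer that all 2 to 10 month-missing deaths are misdated in a way that the recorded year would repair. They are not: most already carry the earliest compatible date.

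A reader might also infer a bias in the hazard ratio, since on-treatment visits are every 2 weeks in one arm and every 3 weeks in the other. The documents do not support this. The rule and the survival follow-up schedule are the same in both arms, and nothing points to unequal rates of missing months. The simulation assumed equal rates, so it cannot show an arm difference either way.

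Nor is 98 days a ceiling. It is a scheduled interval, and deaths traced after loss of contact can have longer gaps, which is why gaps up to 12 months were included.

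**Conclusion.** The rule is wrong as written, in one narrow case: month missing, year of death recorded, and last contact in an earlier calendar year. There it produces a primary-endpoint date that the record excludes. About 0 to 3 of 482 deaths would be redated, assuming that 0.5% to 2% of deaths lack a month and that gaps run from 0-3 up to 0-12 months. Neither assumption comes from the documents. The effect on median OS and power is negligible even at higher shares, and no direction for the hazard ratio can be claimed. The primary test is not at risk. This is a low-priority correction, worth making because the recorded year settles the point without any guess.

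**What to change.** In SAP section 8, replace the rule for a missing month or year with:

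> If the month is missing but the year of death is recorded, the death date is the later of 1 January of that year and the last known date alive. If the year is missing, or the date is completely missing, the last known date alive is used.

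The second sentence also covers a recorded month without a year, so no case is left without a rule. The existing condition on a completely missing date, that a reason for death is present, can stay. The day-missing rule stays unchanged. It would help to report the number of imputed death dates by arm, which would replace the assumed 0.5% to 2% with a fact.

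The cost is a short SAP text change and one line of derivation code. No new data are needed.
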